# Screening period guidance

To ensure safety of study participants, laboratory values and other eligibility assessments taken at screening visit are valid for a maximum of 35 days. The following rules will be applied for active, nonrandomized participants whose participation in the study must be paused due to exceptional circumstances:

- If screening is paused for less than 35 days from screening to randomization visit: the participant will proceed to the next study visit per the usual SoA, provided that randomization visit must be conducted within 35 days from first screening.
  - The site should conduct the next visit if the participant's eligibility criteria are confirmed, and the site should document the reason for delay.

 Due to the pause in screening, sites should also reconfirm the impacted participant's consent and document this confirmation in the source documentation.

• If screening is paused for more than 35 days from screening to randomization visit: The participant must be discontinued because of screening interruption due to an exceptional circumstance. This is documented as a screen failure in the CRF. The participant can reconsent and be rescreened as a new participant. This rescreen is in addition to the one allowed by the main protocol. The screening procedures per the usual SoA should be followed, starting at screening visit to ensure participant eligibility by randomization visit.

# Adjustments to visit windows

Whenever possible and safe to do so, as determined by the investigator's discretion, participants should complete the usual SoA. To maximize the possibility that these visits can be conducted as on-site visits, the windows for visits may be adjusted, upon further guidance from the sponsor. This minimizes missing data and preserves the intended conduct of the study.

For participants whose visits have extended windows, additional study intervention may need to be provided to avoid interruption and maintain overall integrity of the study.

#### **Documentation**

## Changes to study conduct will be documented

Sites will identify and document the details of how participants, visit types, and conducted activities were affected by exceptional circumstances. Dispensing/shipment records of study intervention and relevant communications, including delegation, should be filed with site study records.

#### Source documents at alternate locations

Source documents generated at a location other than the study site should be part of the investigator's source documentation and should be transferred to the site in a secure and timely manner.

# 10.14. Appendix 14: Abbreviations and Definitions

Term	Definition
Abuse	Use of a study intervention for recreational purposes or to maintain an addiction or dependence
AE	adverse event
AHR	aryl hydrocarbon receptor
ALP	alkaline phosphatase
ALT	alanine aminotransferase
AST	aspartate aminotransferase
anti-HCV	hepatitis C virus antibody
AUC	area under the curve
blinding/masking	A single-blind study is one in which the investigator and/or the investigator's staff are aware of the treatment but the participant is not, or vice versa, or when the sponsor is aware of the treatment but the investigator and/the investigator's staff and the participant are not.
	A double-blind study is one in which neither the participant nor any of the investigator or sponsor staff who are involved in the treatment or clinical evaluation of the subjects are aware of the treatment received.
вмі	body mass index
BSA	body surface area
C max	maximum observed concentration
C min,ss	minimum drug concentration at steady state
CCI	
CIOMS	Council for International Organizations of Medical Sciences
CDC	Centers for Disease Control and Prevention
CKD-EPI	Chronic Kidney Disease Epidemiology Collaboration
СМН	Cochran-Mantel-Haenszel
COA	clinical outcome assessments
Complaint	A complaint is any written, electronic, or oral communication that alleges deficiencies related to the identity, quality, purity, durability, reliability, safety or effectiveness, or performance of a drug or drug delivery system.

Term Definition

**Compliance** Adherence to all study-related, good clinical practice (GCP), and applicable regulatory

requirements.

**CONSORT** Consolidated Standards of Reporting Trials

**CRF** case report form; a printed, optical, or electronic document designed to record all of the

protocol-required information to be reported to the sponsor for each trial participant.

**CSR** clinical study report

CXR chest x-ray

**DLQI** Dermatology Life Quality Index

**DMC** data monitoring committee. A data monitoring committee is a group of independent

scientists who are appointed to monitor the safety and scientific integrity of a human research intervention, and to make recommendations to the sponsor regarding the stopping of a study for efficacy, or for harm, or for futility. The composition of the committee is dependent upon the scientific skills and knowledge required for

monitoring the particular study.

**DSM-5** Diagnostic and Statistical Manual of Mental Disorders, Fifth Edition

**ECG** electrocardiogram

**eCOA** electronic clinical outcome assessments

**ED** early discontinuation

**EDC** electronic data capture

**eGFR** estimated glomerular filtration rate

**Enroll** The act of assigning a participant to a treatment. Participants who are enrolled in the

study are those who have been assigned to a treatment.

**Enter** Participants entered into a study are those who sign the informed consent form directly

**GCP** good clinical practice

**GGT** gamma-glutamyl transferase

CCI

**HBsAg** hepatitis B surface antigen

**HBV** hepatitis B virus

**HCV** hepatitis C virus

**HIV** human immunodeficiency virus

Term Definition

Internal Assessment Committee

IB Investigator's Brochure

IC50 half-maximal inhibitory concentration

**ICE** intercurrent event

**ICF** informed consent form

ICH International Council for Harmonisation

**IEC** Institutional Ethics Committee

**IGRA** interferon gamma release assay

CCI

IMP Investigational Medicinal Product (see also "investigational product")

A medicinal product which is being tested or used as a reference, including as a

placebo, in a clinical trial.

informed consent A process by which a participant voluntarily confirms their willingness to participate in

a particular study, after having been informed of all aspects of the study that are relevant to the participant's decision to participate. Informed consent is documented by

means of a written, signed and dated informed consent form.

**INR** international normalized ratio

**interim analysis** An interim analysis is an analysis of clinical study data, separated into treatment groups,

that is conducted before the final reporting database is created/locked.

investigational product

A pharmaceutical form of an active ingredient or placebo being tested or used as a reference in a clinical trial, including products already on the market when used or assembled (formulated or packaged) in a way different from the authorized form, or marketed products used for an unauthorized indication, or marketed products used to

gain further information about the authorized form. See also "IMP."

IRB Institutional Review Board

intent to treat: The principle that asserts that the effect of a treatment policy can be best

assessed by evaluating on the basis of the intention to treat a participant (that is, the planned treatment regimen) rather than the actual treatment given. It has the consequence that participant allocated to a treatment group should be followed up, assessed, and analyzed as members of that group irrespective of their compliance to the

planned course of treatment.

**IWRS** interactive web-response system

CCI

**LDH** lactate dehydrogenase

Term Definition

CCI

medication error

**MAD** multiple ascending dose

Errors in the prescribing, dispensing, or administration of a study intervention, regardless of whether or not the medication is administered to the participant or the error leads to an AE. Medication error generally involve a failure to uphold one or more of the five "rights" of medication use: the right participant, the right drug, the right dose, right route, at the right time.

In addition to the core five rights, the following may also represent medication errors:

- dose omission associated with an AE or a product complaint
- dispensing or use of expired medication
- use of medication past the recommended in-use date
- dispensing or use of an improperly stored medication
- use of an adulterated dosage form or administration technique inconsistent with the medication's labeling (for example, Summary of Product Characteristics, IB, local label, protocol), or
- shared use of cartridges, prefilled pens, or both.

misuse Use of a study intervention for self-treatment that either is inconsistent with the

prescribed dosing regimen, indication, or both, or is obtained without a prescription

mITT modified intent to treat

**MMRM** mixed-effects for repeated measures

**NRI** nonresponder imputation

participant Equivalent to CDISC term "subject": an individual who participates in a clinical trial,

either as recipient of an investigational medicinal product or as a control

PASI Psoriasis Area and Severity Index

PatGA Psoriasis Patient's Global Assessment of Psoriasis

PC product complaint

**PCR** polymerase chain reaction

PDE-4 phosphodiesterase-4

**PK/PD** pharmacokinetics/pharmacodynamics

**PPD** purified protein derivative

**PSS** Psoriasis Symptoms Scale

116

Term Definition

**PSSI** Psoriasis Scalp Severity Index

CCI

QTc corrected QT interval

**SAD** sequential single ascending dose

**SAE** serious adverse event

**SAP** statistical analysis plan

**SCID** severe combined immunodeficiency disease

**screen** The act of determining if an individual meets minimum requirements to become part of

a pool of potential candidates for participation in a clinical study.

**SERMs** selective estrogen receptor modulators

**SoA** schedule of activities

**SOC** system organ class

sPGA Static Physician's Global Assessment

**SUSAR** suspected unexpected serious adverse reaction

TB tuberculosis

TBL total bilirubin level

**ULN** upper limit of normal

**TEAE** Treatment-emergent adverse event: An untoward medical occurrence that emerges

during a defined treatment period, having been absent pretreatment, or worsens relative to the pretreatment state, and does not necessarily have to have a causal relationship

with this treatment.

Th T helper

**TST** tuberculin skin test

**WBC** white blood cells

**WNOCBP** women of childbearing potential

**WOCBP** women not of childbearing potential

# 10.15. Appendix 15: Protocol Amendment History

The Protocol Amendment Summary of Changes Table for the current amendment is located directly before the Table of Contents (TOC).

Amendment [a]: 31-Oct-2023

## **Overall Rationale for the Amendment:**

The primary purpose of this amendment is to modify the study to a staged design that enables the evaluation of a high dose of LY3972406 initially in Stage 1. Depending on the results of this evaluation, a lower dose potentially may then be evaluated in Stage 2.

Section # and Name	Description of Change	Brief Rationale
Title Page	Updated the brief title.	To shorten the existing brief title.
1.1. Synopsis		
Title Page 1.1. Synopsis	Deleted EU Trial number.	Not required, since the study will run only in the US.
1.1. Synopsis	
 
Added the details of modified study design including Stage 1 and 2 in Overall design.
 
Updated the number of participants.
 
Updated the intervention groups as per the modified study design including Stage 1 and 2.
 
	To modify the study to a staged design that enables evaluation of a high dose of LY3972406 initially in Stage 1 and depending on the interim analysis results, a lower dose later at Stage 2.
1.2. Schema	Added new data schema to include both Stage 1 and Stage 2 of the modified study design.	To align with the modified study design.
1.3.1. Schedule of Activities for the Screening and Treatment Periods of Study J4H-MC-FVAA	Updated the comment in Patient- reported outcomes to include "clinician-administered" assessments.	For clarification.
1.3.2. Schedule of Activities for ED, Unscheduled Visits, and Post-Treatment Follow-up of Study J4H-MC-FVAA		
2.2. Background	In Preclinical safety, added information for toxicological findings in	To update the toxicological findings in the study preclinical safety information.
2.3.3. Overall Benefit Risk Conclusion	Added text regarding that study has 2 stages and approximately an additional participants will be enrolled in Stage 2.	To align with the modified study design.
4.1. Overall Design	Added the details of modified study design including Stage 1 and 2.	To modify the study to a staged design that enables evaluation of a high dose of LY3972406 initially in Stage 1 and depending on the interim

Section # and Name	Description of Change	Brief Rationale
		analysis results, a lower dose later at Stage 2.
6.1. Study Intervention(s) Administered	For LY3972406 CCl added that it is used only in Stage 2.	For clarification.
6.1. Study Intervention(s) Administered	In table listing the study interventions, deleted the last row for EU authorization.	Not required, since the study will run only in the US.
9.4. Interim Analyses	Added the details of database lock and interim analysis for Stage 1 and Stage 2.	To align with the modified study design.
9.5. Sample Size Determination	Updated the sample size calculation based on the updated number of participants.	To align with the modified study design.
10.1.5. Committees Structure	Added that the IAC will determine if Stage 2 will be initiated, pending results of the interim analysis.	For clarification.
10.1.6. Dissemination of Clinical Study Data	Deleted "EU" from the Data section.	Not required, since the study will run only in the US.
10.4.2. Contraception Guidance	Added the heading for the table describing different forms of contraception in male and female participants.	For clarification.
10.9. Appendix 9: Photography	Deleted the statement mentioning that the study sites may include sites in EU Member States and other regions.	Not required, since the study will run only in the US.
10.13. Appendix 13: Country-specific Requirements	Deleted the Germany-specific protocol requirements.	For clarification, since the study will run only in the US.
10.15. Appendix 15: Abbreviations and Definitions	Deleted the abbreviation of EU.	Not required, since the study will run only in the US.
Throughout the protocol	Minor formatting and editorial changes.	Minor, therefore, not detailed.

# Version history

This Statistical Analysis Plan (SAP) for Study J4H-MC-FVAA (FVAA) is based on the protocol dated 31 October 2023.

# **SAP Version History Summary**

SAP Version	Approval Date	Change	Rationale
1	See date on Page 1	Not Applicable	Original version

[figure not shown]
# 1. Introduction

Study J4H-MC-FVAA (FVAA) is a Phase 2, randomized, double-blind, placebo-controlled study to investigate the efficacy and safety of LY3972406 in adults with moderate-to-severe plaque psoriasis.

There are no changes to the analyses described in the protocol.

1.1. Objectives, Endpoints, and Estimands

Objectives, Enupoints,	
Objectives	Endpoints
Primary	
To compare the efficacy of     LY3972406 versus placebo in the     treatment of participants with     moderate-to-severe plaque psoriasis	Proportion of participants achieving PASI 75 at Week 12
Secondary	
To compare the efficacy of LY3972406 versus placebo, as measured by improvement in clinical signs and symptoms	
 
Proportion of participants achieving the following at Week 12         
 
PASI 90
 
PASI 100
 
sPGA 0 (clear), or
 
sPGA 0 or 1 (clear or almost clear).
 
 
 
PASI percent change from baseline to Week 12
 
BSA mean change from baseline to Week 12
 
Proportion of participants who achieve a PSSI score of 0 at Week 12
 
PSSI mean change from baseline to Week 12a
 

To compare patient-reported outcomes from participants who received LY3972406 to those who received placebo	
 
Mean change from baseline to Week 12 for quality-of-life measures
 
DLQI
 
PatGA Psoriasis, and
 
PSS
 

To characterize the PK of     LY3972406	Observed trough LY3972406 plasma concentration at Week 12
To describe the safety of     LY3972406 in participants with     psoriasis	Summary of safety data, including number and incidence of  SAEs TEAEs Discontinuations due to AE

Abbreviations: AE = adverse event; BSA = body surface area; DLQI = Dermatology Life Quality Index; IL = interleukin; PASI = Psoriasis Area and Severity Index; PatGA Psoriasis = Patient's Global Assessment of Psoriasis; PK = pharmacokinetics; PSS = Psoriasis Symptoms Scale; PSSI = Psoriasis Scalp Severity Index; SAE = serious adverse event; sPGA = Static Physician's Global Assessment; TEAE = treatment-emergent adverse event.

a Only for participants with baseline scalp psoriasis involvement, defined as baseline PSSI >0.

#### Primary and secondary estimands

The primary clinical question of interest is

What is the difference between each dosing regimen of LY3972406 and placebo in the target patient population in achieving a successful response without the use of prohibited concomitant medication or discontinuing the study intervention either due to lack of efficacy or due to an AE?

The efficacy estimands are described by the following attributes:

- Estimand strategy
  - Binary endpoints: hybrid of composite variable and treatment policy estimands (conditional)
  - o Continuous endpoints: hypothetical (unconditional)
- Population: Adults with moderate-to-severe plaque psoriasis
- Endpoints
  - Binary: Psoriasis Area and Severity Index (PASI) 75 (primary), PASI 90,
     PASI 100, Static Physician's Global Assessment (sPGA) 0 (clear), sPGA 0 or 1 (clear or almost clear), and Psoriasis Scalp Severity Index (PSSI) 0
  - Continuous: PASI, body surface area, Dermatology Life Quality Index, Patient's Global Assessment of Psoriasis, PSSI, and Psoriasis Symptoms Scale
- Timepoints: Week 12 for all endpoints

- How to account for intercurrent events (ICEs):
  - o ICEs related to study intervention include the use of prohibited concomitant medication and early discontinuation from the study or study intervention due to lack of efficacy or an adverse event (AE). Participants with ICEs related to study intervention will be considered as a treatment failure (binary endpoints) or missing at random (continuous endpoints) from the time of the ICE.
  - For all remaining ICEs, a treatment policy strategy will be used. That is, the observed data will be used regardless of whether ICEs unrelated to study intervention have occurred.
- Population-level summary:
  - o Binary endpoints: Difference in proportion of participants achieving response between each dosing regimen of LY3972406 and placebo
  - Continuous endpoints: Mean difference between each dosing regimen of LY3972406 and placebo
- Rationale for the primary estimand:
  - o If a participant used any prohibited concomitant medication for plaque psoriasis, the participant was not receiving sufficient benefits from the study intervention.
  - o If a participant discontinued early from the study intervention due to lack of efficacy or an AE, the participant experienced a burden of the study intervention that outweighed its benefits.
  - o All remaining ICEs are considered unrelated to the study intervention.

The safety estimand will be evaluated on each dosing regimen of LY3972406 and placebo on the safety analysis set. The estimand is described with the following attributes:

- Population: Adults with moderate-to-severe plaque psoriasis who had at least 1 dose of the study intervention
- Endpoints: serious adverse events (SAEs), treatment-emergent adverse events (TEAEs), and discontinuations due to AE
- Timepoints: All aggregated timepoints
- Population-level summary: Proportion of participants experiencing the safety endpoint

The occurrence of ICEs is irrelevant.

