## 1.2. Schema

Abbreviations: ED = early discontinuation; n = number of participants; CCI; V = visit; W = week.

For randomization ratios, see Section 4.1.

<sup>a Visits 803 and 804 are not required for all participants (see Section 7.2 for details).

<sup>b For the follow-up visits, the weeks in parentheses indicate weeks after the last dose.

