## 7.1.3. Permanent Discontinuation of Study Intervention

When necessary, a participant may be permanently discontinued from study intervention. If so, the participant will discontinue the study intervention (treatment), thereby discontinuing the treatment period, and will remain in the study to complete procedures for an ED visit and post-treatment follow-up as shown in the SoA.

Possible reasons leading to permanent discontinuation of study intervention include, but are not limited to, the following:

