# Participant decision

• The participant requests to discontinue the study intervention.

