# Hematologic test abnormality: CCl

**Noncompliance:** The investigator decides the participant is noncompliant with study drug administration or any other study procedure.

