#### Handling of missing, unused, and spurious data

Handling of missing, unused, and spurious data is addressed prospectively in the overall statistical methods described in the protocol and in this document, where appropriate. Adjustments to the planned analyses are described in the final clinical study report.

Missing data imputation is not to be confused with estimand strategy. Missing data of categorical efficacy, patient-reported outcomes, and quality-of-life variables will be imputed using a nonresponder imputation (NRI) method, and the missing data will be considered as nonresponder. For continuous variables, missing data will not be imputed.

When NRI is applied, participants with missing data will be considered as nonresponders regardless of whether they have at least 1 postbaseline data.

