# 4.3. Primary Estimand Analysis

Treatment comparisons between each LY3972406 dose and placebo in the proportion of participants achieving PASI 75 at Week 12 will be analyzed using the Cochran-Mantel-Haenszel

test stratified by prior exposure to biologic therapy for psoriasis (biologic naïve versus experienced) with NRI, as described. Participants who fail to complete the 12-week treatment period due to an ICE related to study intervention or violate the concomitant medications rules will be treated as nonresponders. The 95% confidence intervals associated with the treatment response rate and treatment difference to placebo will be provided by treatment. The primary analysis will be conducted on the modified intent-to-treat analysis set when all participants reach Week 12 or have discontinued during the treatment period.

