# 4.9. Interim Analyses

Analyses for the primary database lock will be conducted as described in Section 9.3 of the protocol. If Stage 2 is not initiated, the primary outcome database lock will occur when all the participants from Stage 1 have completed the Week 12 visit or have discontinued the study intervention. If Stage 2 is initiated, the primary outcome database lock will occur when all the participants from Stage 2 have completed the Week 12 visit or have discontinued the study intervention.

Two interim analyses may be conducted during Stage 1 prior to the primary database lock at the sponsor's discretion. One interim may occur when approximately 50% to 90% of participants from Stage 1 have completed the Week 12 visit or have discontinued the study intervention. Another interim analysis may be conducted when approximately 90% to 100% of participants from Stage 1 have completed the Week 12 visit or have discontinued the study intervention. The results of either interim analysis can be used by the sponsor's internal assessment committee (IAC) to recommend if Stage 2 should be initiated.

The interim analyses may include safety, PK, PD, and efficacy data. The data may be used for internal decision making, development of PK and PD modeling, or both. An assessment of unblinded interim data will be conducted by an IAC with a limited number of individuals who do not have direct site contact or data entry or validation responsibilities. Study sites will receive information about interim results only if they need to know for the safety of their participants.

The study will not be stopped early due to efficacy.

Unblinding details are specified in the blinding unblinding document.

At the discretion of the sponsor, prespecified interim analyses may not be conducted.

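### Treatment policy is declared for permanent discontinuation for other reasons, but no Week 12 value is kept after stopping, so nonresponder imputation scores these participants as failures

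*SAP*

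**What the plan says.** Protocol Section 3 and SAP Section 1.1 divide intercurrent events into two groups for the binary endpoints (PASI 75, 90 and 100, sPGA 0 and 0/1, PSSI 0), all at Week 12.

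- **Related to study intervention:** prohibited concomitant medication, and early discontinuation due to lack of efficacy or an adverse event. These count as treatment failure.
- **Everything else:** "For all remaining ICEs, a treatment policy strategy will be used", with observed data used despite the event.

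SAP 4.3 keeps this split. Besides breaches of the concomitant-medication rules, the participants it sets to nonresponse are "Participants who fail to complete the 12-week treatment period due to an ICE related to study intervention". SAP 4.4 does the same for the secondary binary endpoints.

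Protocol 7.1.3 lists reasons for permanent discontinuation that belong to the second group by exclusion, for example "The participant requests to discontinue the study intervention" and "The investigator decides the participant is noncompliant with study drug administration or any other study procedure". It also says what happens next: the participant stops treatment, "thereby discontinuing the treatment period, and will remain in the study to complete procedures for an ED visit and post-treatment follow-up". The note to the schema (Protocol 1.2) gives the timing: "For the follow-up visits, the weeks in parentheses indicate weeks after the last dose".

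On missing data, SAP 4.1 states: "When NRI is applied, participants with missing data will be considered as nonresponders regardless of whether they have at least 1 postbaseline data".

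**The concern.** A treatment-policy strategy needs the outcome to be measured after the event, at the endpoint time. Here the visit schedule removes that measurement for one class of event, and the missing-data rule then supplies a failure. If so, related and unrelated permanent discontinuations receive the same primary outcome, although the estimand separates them on purpose: its rationale calls the remaining events unrelated to the study intervention. The study report would describe the PASI 75 difference as a composite/treatment-policy hybrid, while the analysis behind it counts permanent discontinuation for any reason as failure.

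**Working it through.** **Tracing a participant who permanently stops at their own request, not for efficacy or safety**

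1. *Strategy.* Not on the related list, so treatment policy with observed Week 12 data (Protocol 3, SAP 1.1).
2. *Visits.* The treatment period ends. An early discontinuation visit follows, then Visits 801 to 804 at 2, 4, 8 and 12 weeks after the last dose (Protocol 1.3.2, 7.1.3). Visit 9 is not kept.
3. *Data.* PASI, sPGA and, for participants with baseline scalp involvement, PSSI are collected at those visits (Protocol 1.3.2). Neither SAP 4.1 nor the endpoint table in SAP 4.8.1 contains an analysis window or a rule turning such a value into Week 12.
4. *Derivation.* PASI 75 is missing when the observed value is missing (SAP 4.8.1).
5. *Imputation.* Missing becomes nonresponse (SAP 4.1).

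On the current text, every such participant is therefore a failure. Temporary interruptions are unaffected, because those participants stay on the visit schedule.

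**Would a mapping rule alone be enough?**

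Inputs from Protocol 1.3: Visit 9 target 84 days after randomisation, ±3 (window 81 to 87); follow-up offsets from last dose 14 ±3, 28 ±3, 56 ±7 and 84 ±7 days. Let d be the day of last dose after randomisation, d = 1 to 80. Weighting these days equally is an assumption.

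| Question | Last-dose days d | Count |
|---|---|---|
| Nominal follow-up date falls in 81–87 | 1–3 (V804), 25–31 (V803), 53–59 (V802), 67–73 (V801) | 24/80 = 30% |
| Some date within tolerance falls in the window | all except 11–17, 39–49, 63, 77–80 | 57/80 = 71% |
| Whole tolerance range lies in the window | 56 (V802), 70 (V801) | 2/80 |

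Example: a last dose at Week 6 puts follow-up at Weeks 8, 10, 14 and 18. An early discontinuation visit 3 or 7 days after the last dose raises the 24 to 27 or 31. Including d = 0 gives 25/81 and 58/81. Visits 803 and 804 are skipped only when the previous PASI is at or above baseline, where nonresponse is very probably true, so they are counted. With a mapping rule but no retained visit, 80 − 24 = 56 of 80 stop days (70%) still give no nominal value.

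**Effect on the PASI 75 difference**

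The plan has no figure to reproduce: the sample size, power and response rates are redacted, and no discontinuation rate is given. Let q be the share of an arm stopping permanently for unrelated reasons, and r their true off-drug Week 12 PASI 75 rate. Nonresponder imputation lowers the arm's rate by q × r, so with A for active and P for placebo:

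shift = −100 × (qA·rA − qP·rP) percentage points.

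All values of q and r below are assumptions.

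| qA / qP | rA / rP | Arithmetic | Shift |
|---|---|---|---|
| 5% / 5% | 20% / 5% | −100(0.0100 − 0.0025) | −0.75 |
| 5% / 5% | 40% / 5% | −100(0.0200 − 0.0025) | −1.75 |
| 5% / 5% | 50% / 0% | −100(0.0250 − 0) | −2.5 |
| 2% / 2% | 20% / 5% | −100(0.0040 − 0.0010) | −0.3 |
| 2% / 2% | 40% / 5% | −100(0.0080 − 0.0010) | −0.7 |
| 2% / 2% | 50% / 0% | −100(0.0100 − 0) | −1.0 |
| 2% / 5% | 10% / 5% | −100(0.0020 − 0.0025) | +0.05 |

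The shift is zero whenever q·r is equal in the two arms. With a mapping rule only, and r unrelated to stop day, the 5% rows are multiplied by 56/80 = 0.70: −0.53, −1.23 and −1.75.

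**The case against.** - **Imputation is not estimand strategy.** Both documents say so, and the primary analysis is announced as using nonresponder imputation. That defends the rule for sporadic missing values. Here the protocol's own schedule creates the gap, for people it expects to remain in the study.
- **A follow-up PASI taken 12 weeks after randomisation could be read as observed Week 12 data.** No rule says so. Protocol 9.3.5 and SAP 4.7.2 equate Week 12 with Visit 9 and set it apart from early discontinuation. Without a rule the choice falls to whoever programs the endpoint.
- **SAP 4.1 makes the lock wait for 100% of primary endpoint data.** The triggers elsewhere count a discontinued participant as finished: SAP 4.9 waits until participants "have completed the Week 12 visit or have discontinued the study intervention", and SAP 4.3 is similar. Nothing creates a later assessment to wait for.
- **The group is narrow and the effect small.** This stands. Many listed stopping reasons would be adverse events or prohibited medication, which are failures by design, and participants lost to follow-up would have no value under any schedule. Protocol 7.2 expects discontinuation to be uncommon, though that section concerns withdrawal from the study rather than stopping treatment. With an assumed 30 per arm and true rates of 40% versus 5%, 5% stopping per arm with r of 30% versus 5% moves power only from 0.92 to 0.91.

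**Conclusion.** The concern holds. For permanent discontinuation not due to lack of efficacy, an adverse event or prohibited medication, the declared treatment-policy strategy is not carried out for the binary endpoints, and the literal analysis is composite failure. This rests on the text alone. The size rests on assumed rates and is probably small; it usually shrinks the difference, but the direction is not fixed. The plan should be corrected because this is the primary endpoint and its reported estimand would not match its analysis. Nothing here suggests that the trial could not be interpreted.

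**What to change.** Either of two changes resolves it.

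**1. Keep the estimand and collect the data.**
- For participants who permanently stop study intervention but remain in the study, retain PASI, sPGA and (where applicable) PSSI at 12 weeks from randomisation within the Visit 9 tolerance. Combine this with an early discontinuation or follow-up visit when one falls there.
- Add to SAP 4.1 a rule limited to these participants: a value within that tolerance is analysed as Week 12 for binary endpoints unless a related intercurrent event has occurred. State the day convention (the target is Day 85 if first dosing is Day 1). Completers' Visit 9 values, including those with windows adjusted under Protocol 10.13, stay as they are.
- Align the analysis and lock triggers (Protocol 9.3.2 and 9.4; SAP 4.1, 4.3 and 4.9) so that they wait for this assessment.
- Report by arm how many of these values were observed or imputed, and state that nonresponder imputation applies to those who leave the study.

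Cost: a schedule change, one SAP rule, a check of the triggers, and an added or re-timed visit for a few people. Adding a visit rather than moving one preserves follow-up timed from last dose.

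**2. Restate the estimand.** In Protocol 3 and SAP 1.1 (including the clinical question), and in the analysis text (Protocol 9.3.2 and 9.3.3; SAP 4.3 and 4.4), make permanent discontinuation for any reason a composite failure for binary endpoints. Keep treatment policy only for events after which Week 12 is still assessed. Cost: wording only, but possibly a protocol amendment if the primary estimand counts as a principal feature under Protocol 9.3.1.
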